10.1 Multiplicity

Gate-keeping methods were used to control the overall Type 1 error rate for the key secondary endpoints. After the result from the primary efficacy analysis in the ITT population showed statistical significance, the key secondary endpoint 1 was tested next. The key secondary endpoint 2 was tested only if the test results for both primary endpoint and the key secondary endpoint 1 were significant. The key secondary endpoint 3 was tested only if the test results for primary endpoint and the key secondary endpoints 1 and 2 were all significant. The testing procedure above was implemented strictly in order to control the overall Type 1 error rate of 0.05 due to multiplicity. Details regarding the gate-keeping methods are described in Section 10.1.

10.2 Completed Analysis of Primary Efficacy Endpoint

The primary endpoint response rate is defined as the number of responders (subjects who achieve an erythroid response during the 12-week interval from Week 13 to Week 24 compared to baseline) divided by the number of subjects in the ITT population within each treatment group. The

erythroid response is defined as subjects with $\geq 33\%$ reduction from baseline in RBC transfusion burden with a reduction of at least 2 units, where the 12-week interval on or prior to Dose 1 Day 1 is used as baseline value. Specifically, if a subject is not treated, the 12-week interval on or prior to randomization date will be used as baseline value.

The 12-week RBC transfusion burden (units/12 weeks) is calculated as Number of RBC units transfused during the 12-week interval.

The following statistical hypothesis was tested:

$H_0: P_1$ (response rate in the luspatercept group) = P_2 (response rate in the placebo group)

$H_a: P_1 \neq P_2$

The treatment comparison (luspatercept plus BSC versus placebo plus BSC) was conducted by the Cochran Mantel-Haenszel (CMH) test stratified by the geographical regions defined at randomization as stratification factor. The odds ratio (OR) (luspatercept versus placebo) with corresponding 2-sided (at 0.05 alpha level) 95% CI and p-value was provided.

The number and percentage of responders were summarized by each treatment group and the difference in proportions (luspatercept – placebo) and corresponding 95% CI were also calculated by unconditional test.

A forest plot showing the ORs, 95% CI and p-value for the overall result and the results in each subgroup was constructed.

Listing of individual RBC transfusion data was provided.

No further analysis for the primary efficacy endpoints will be included in the final CSR.

10.3 Completed Analyses of Key Secondary Efficacy Endpoints

The completed key secondary endpoints are:

1. Proportion of subjects with hematological improvement, defined as $\geq 33\%$ reduction from baseline in RBC transfusion burden with a reduction of at least 2 units from Week 37 to Week 48.
2. Proportion of subjects with hematological improvement, defined as $\geq 50\%$ reduction from baseline in RBC transfusion burden with a reduction of at least 2 units from Week 13 to Week 24.
3. Proportion of subjects with hematological improvement, defined as $\geq 50\%$ reduction from baseline in RBC transfusion burden with a reduction of at least 2 units from Week 37 to

Week 48.

4. Mean change in transfusion burden (RBC units/12 weeks) from Week 13 to Week 24.

To control the overall Type 1 error rate for the endpoints 1~3, the testing procedure was implemented strictly in order: the test for 33% hematological improvement from week 37 to week 48 (endpoint 1) would only be conducted when there was evidence showing that erythroid response was achieved in the luspatercept group from week 13 to week 24 (primary endpoint); the test for 50% hematological improvement from week 13 to week 24 (endpoint 2) would only be conducted when there was evidence showing that erythroid response was achieved in the luspatercept group from week 13 to week 24 (primary endpoint) and 33% hematological improvement was achieved in the luspatercept group from week 37 to week 48 (endpoint 1); the test for 50% hematological improvement from week 37 to week 48 (endpoint 3) would only be conducted when there was evidence showing that erythroid response was achieved in the luspatercept group from week 13 to week 24 (primary endpoint), the 33% hematological improvement was achieved in the luspatercept group from week 37 to week 48 (endpoint 1) and the 50% hematological improvement was achieved in the luspatercept group from week 13 to week 24 (endpoint 2).

For the first three secondary endpoints, the number and percentage of responders in ITT population were summarized by treatment group and the treatment comparison was analyzed analogous to the primary efficacy endpoint, using the CMH model stratified by the geographical regions defined at randomization.

The OR (luspatercept versus placebo) with corresponding 2-sided (at 0.05 alpha level) 95% CI and p-value was provided. The difference in proportions (luspatercept – placebo) was also calculated. A forest plot showing the ORs, 95% CI and p-value for the overall result and the results in each subgroup was constructed for each endpoint.

The fourth secondary endpoint, mean change in RBC transfusion burden at the 12-week interval of Week 13 to Week 24 from the baseline 12-week interval, was analyzed using analysis of covariance (ANCOVA) with baseline values and geographical regions defined at randomization taken as covariates for the ITT population. Treatment effect was evaluated as a contrast of luspatercept versus placebo. Least squares (LS) means with corresponding standard errors (SE) for each treatment group, along with LS mean of treatment difference with corresponding 95% CI and p-value were presented. Also, summary statistics for RBC transfusion burden, change from baseline and percent change from baseline in RBC transfusion burden were provided by treatment group for the following 12-week intervals: Week 1 to Week 12, Week 13 to Week 24, Week 25 to Week 36, and Week 37 to Week 48.

The totality of transfusion burden reduction was evaluated using 24 weeks baseline (sum of 12 weeks historical data and 12 weeks run in data). Baseline of 48 weeks transfusion burden was defined as 2 times 24 weeks baseline transfusion burden. Descriptive statistics (n, mean, median, SD, range) for totality of transfusion burden reduction along with the change from baseline were summarized for each treatment group by 24 weeks and 48 weeks. Only subjects whose efficacy cutoff date was on or beyond end of the week 24/48 interval were included in the analysis.

A waterfall plot was provided for the 24-week post-baseline transfusion burden percent change from baseline by treatment group and time point. Individual subject's transfusion burden percent change from baseline was displayed in a single bar.

No further analysis for key secondary efficacy endpoints will be included in the final CSR.

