## 9.6. Efficacy Analysis

### 9.6.1. Primary Efficacy Analysis

The efficacy analysis will be performed on the ITT population. The primary efficacy analysis will be performed based on 24 weeks of data after all subjects have completed the double-blind 24-week treatment period phase or discontinued before reaching 24 weeks of double-blind treatment (for this study one month equal to 4 weeks is considered). A higher response rate in the luspatercept over placebo and a p-value < 0.05 will confirm the superiority of luspatercept in the efficacy.

The primary efficacy endpoint of this study is defined as subjects with  $\geq 33\%$  reduction from baseline in RBC transfusion burden with a reduction of at least 2 units from Week 13 to Week 24 compared to the 12-week interval prior to randomization for luspatercept plus BSC versus placebo plus BSC.

For the early discontinued subjects, ie, who did not complete 24 weeks of double-blinded treatment period, the transfusion records will still be collected up to 48 weeks. All the transfusion records will be used to evaluate primary and secondary endpoints.

The first day to be used for statistical analysis will be defined as the date of the first dose. A transfusion received on Dose 1 Day 1 will be counted in the baseline transfusion burden.

The primary endpoint response rate is calculated using the number of responders divided by all subjects in the ITT population. The response rates of the subjects who randomized to luspatercept and the placebo will be calculated. Let  $P_1$  denote the true response rate in the luspatercept group, and  $P_2$  denote the true response rate in the placebo group. In the primary efficacy analysis, the statistical hypothesis is

$$H_0 : P_1 = P_2$$

$$H_a : P_1 \neq P_2$$

The number and percentage of subjects in the ITT population who achieve the response will be calculated for luspatercept and placebo. The difference in proportions between luspatercept and placebo will be calculated and the Cochran Mantel-Haenszel (CMH) chi-square test would be performed using randomization factors as strata, corresponding 95% confidence interval (CI)

associated with the test will be provided. A higher response rate in the luspatercept arm over placebo arm with a p-value < 0.05 will infer that luspatercept is significantly superior to placebo.

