10. EFFICACY ANALYSIS

All efficacy evaluations are conducted using the ITT population, with the exception of Quality of Life analyses that are conducted on the HRQoL evaluable population. Statistical comparisons are made between luspatercept plus BSC vs. placebo plus BSC. Key secondary efficacy results are considered statistically significant after consideration of the strategy for controlling the family-wise Type 1 error rate, as described in Section 10.1, Multiplicity. All statistical tests are 2-sided at the significance level of $\alpha = 0.05$, and the corresponding p-values and 2-sided CIs for point estimates are reported, unless specified otherwise.

For the early treatment discontinued subjects, i.e., patients who did not complete 24 weeks or 48 weeks of double-blinded treatment period, the transfusion records were collected up to 48 weeks or 9 weeks post last dose, whichever was the later date. All the transfusion records collected throughout the entire study period up to the efficacy cutoff date were used in the RBC related efficacy analyses. The efficacy cutoff date for the primary CSR was defined as the minimum date among death date, study discontinuation date, last dose date + 20, and 11MAY2018. For the primary and key secondary endpoints, if at the time of data summary, a subject's efficacy cutoff date was before the end of the 12-week interval or a subject had any invalid transfusion records (i.e., transfusion unit not available) during the specified 12-week interval, this subject was included in the analysis as a non-responder.

All the efficacy analysis for the final CSR will not include the assessments for the placebo patients who crossed over to luspatercept. In other words, the assessments for the placebo patients will be analyzed up to the cross-over timepoint. For those subjects in the original luspatercept treatment, their assessments will be analyzed until the new efficacy cutoff date which is defined as the minimum date among death date, study discontinuation date, last dose date + 20.

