10.7 Missing Data Imputation

In case of any missing data for RBC transfusion units records and MRI liver iron content, imputation will be applied for each section.

The imputation for RBC transfusion units is stated in Section 10: if at the time of data summary, a subject's efficacy cutoff date is before the end of the 12-week interval or a subject has any invalid transfusion records (i.e., transfusion unit not available) during the specified 12 week interval, this subject will be included in the analysis as a non-responder.

The imputation logic for missing LIC value is stated in Section 10.5.2: the value of LIC will be either the value collected from eCRF or the value derived from T2*, R2* or R2 parameters depending on which techniques and software were used for MRI LIC data acquisition.

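### Key secondary endpoint 4 (mean change in units, Weeks 13 to 24) has no usable rule for subjects whose window is cut short, and the SAP's record cutoff conflicts with the protocol's promise to use all their records

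*SAP*

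**What the plan says.** - **Model.** SAP 10.3 says that endpoint 4, the change in 12-week burden from baseline to Weeks 13 to 24, "was analyzed using analysis of covariance (ANCOVA) with baseline values and geographical regions defined at randomization taken as covariates for the ITT population". It states no completeness restriction, proration or imputation for this model.
- **Records.** SAP 10: "All the transfusion records collected throughout the entire study period up to the efficacy cutoff date were used in the RBC related efficacy analyses". The cutoff for the primary CSR "was defined as the minimum date among death date, study discontinuation date, last dose date + 20, and 11MAY2018".
- **Burden.** SAP 10.2: the 12-week burden "is calculated as Number of RBC units transfused during the 12-week interval". SAP 5.1 sets the window at Day 86 to Day 169, which is 84 days.
- **Incomplete windows.** For the primary and key secondary endpoints, SAP 10 says that if the cutoff precedes the end of the interval, "this subject was included in the analysis as a non-responder". SAP 10.7 repeats this and adds nothing for a unit count.
- **A neighbouring analysis.** The descriptive totality summary in SAP 10.3 is limited to subjects whose cutoff reaches the end of the interval.
- **Protocol.** Section 9.6.1 says that transfusion records of subjects who stop before 24 weeks are still collected up to 48 weeks, and then: "All the transfusion records will be used to evaluate primary and secondary endpoints". SAP 10 confirms the collection, to Week 48 or 9 weeks after the last dose, whichever is later.

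**The concern.** The non-responder rule does its work for the primary endpoint and key secondaries 1 to 3: time that is not counted cannot turn into a response. Endpoint 4 is a number of units, and being a non-responder does not supply one. What remains is a raw count, cut at the efficacy cutoff, in a model for all randomized subjects. On that reading, time that is not counted looks like time without transfusion, so an early stopper scores worst on the binary endpoints and may score well on endpoint 4.

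The alternative is that the programmers set such subjects to missing. They then fall out of the ANCOVA, the analysis is not ITT, and that rule is unwritten too. Either way the plan does not determine the result, and either way it sets aside records that the protocol says are used. At stake are the arm means, the precision of the comparison and, if drop-out differs between arms, the treatment difference of a key secondary endpoint.

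**Working it through.** **The plan's own figure.** The documents give no SD, effect size or power for endpoint 4. The only sample-size statement concerns the primary endpoint (protocol 9.3, SAP 4.4): 40% versus 20%, 2:1, 90% power, two-sided 0.05, 10% drop-out. With a continuity correction this needs 90 + 180 = 270 subjects, and 270/0.90 = 300, as stated. The 10% drop-out per group is the only drop-out figure available and is used below.

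**Inputs.**
- Window Day 86 to 169, 84 days (SAP 5.1).
- Cutoff = last dose day + 20, the binding date for a subject who stops drug and stays in follow-up (SAP 10).
- Baseline B of 3 to 10 units/12 weeks, half of the 6 to 20 units/24 weeks required for entry (protocol 4.2).
- Assumed: true burden constant at B, so the true change is zero.

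**Step 1: apparent change for one subject.** Observed days = max(0, min(last dose + 20, 169) - 85). Apparent change = B x (observed days/84) - B. With B = 6:

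| Last dose day | Cutoff day | Window days observed | Apparent change (units) | % |
|---|---|---|---|---|
| 65 or earlier | 85 or earlier | 0 | -6.0 | -100 |
| 85 | 105 | 20 | -4.57 | -76 |
| 106 | 126 | 41 | -3.07 | -51 |
| 127 | 147 | 62 | -1.57 | -26 |
| 148 | 168 | 83 | -0.07 | -1 |
| 149 or later | 169 or later | 84 | 0 | 0 |

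**Step 2: arm mean.** Assume the last dose of a stopper is uniform over 168 days. Days 1 to 65 lose the whole window: 65. Days 66 to 148 lose 83/84 down to 1/84: (83 x 84/2)/84 = 41.5. Mean lost fraction = (65 + 41.5)/168 = 0.634. At 10% drop-out the shift is 0.10 x 0.634 x B = 0.063 x B:
- B = 3: -0.19 unit
- B = 7: -0.44 unit
- B = 10: -0.63 unit

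If all stoppers left before the window could count anything, the shift would be 0.10 x B, or -0.3 to -1.0 unit.

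**Step 3: treatment difference.**
- Equal drop-out, no true effect: the shifts cancel and there is no bias.
- Equal drop-out, true effect t that stoppers would also have shown in the window: the difference becomes t x (1 - 0.063), about 6% smaller.
- Unequal drop-out, for example an assumed 15% versus 5%: bias = 0.10 x 0.634 x 7 = 0.44 unit at B = 7, in favour of whichever arm stops more.

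**Step 4: simulation of the ANCOVA.** 2,000 runs, 200:100; assumed baseline mean 6 and SD 1.7, residual SD 1.8, stop day uniform over Days 1 to 148, stoppers without treatment benefit.

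| Drop-out, luspatercept/placebo | True effect in completers | Difference, all records | Difference, truncated | Rejection rate, all records / truncated |
|---|---|---|---|---|
| 10%/10% | 0 | 0.00 | 0.00 | 4% / 5% |
| 15%/5% | 0 | 0.00 | -0.44 | 5% / 31% |
| 5%/15% | 0 | +0.01 | +0.44 | 5% / 36% |
| 10%/10% | -1.0 | -0.89 | -0.89 | 98% / 91% |

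In the first row the standard error rises from 0.22 to 0.28. In the last row stoppers carry no effect, so both estimates agree and the cost is precision only.

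**The case against.** The strongest objection is that nowhere does the SAP say that truncated counts entered the model. Its incomplete-window rule is worded for the primary and key secondary endpoints, and endpoint 4 is listed as a key secondary. So the text puts endpoint 4 under a rule that does not fit it, which is not the same as an instruction to score zero units. This stands. The defect is an undefined rule, and the zero or partial count is its literal consequence, not a documented event. That the totality summary carries its own restriction shows only that endpoint 4 lacks one; it does not show that the problem was noticed and left.

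Second, the analysis was governed by a SAP signed on 19 June 2018, which is not available here. The present SAP describes it in the past tense and plans no further analysis. That stands as well, and it limits what can be asked for now: a re-run is post hoc and unblinded. It does not remove the need for an explanation, because SAP 2 says the primary-CSR analyses are included in the final CSR without update.

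Third, the inferential weight is modest. SAP 10.1 and 10.3 describe Type 1 error control for key secondaries 1 to 3. SAP 4.2.2.1 and protocol 9.6.2 place endpoint 4 in the sequence too, but last, so no later test depends on it.

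Fourth, the false difference of about 0.44 unit needs a drop-out imbalance that no document reports. With the planned equal 10% there is none under the null. This stands; 15% versus 5% is illustration only.

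**Conclusion.** The plan leaves endpoint 4 undefined for subjects whose Week 13 to 24 window is cut short, and the cutoff that shortens it contradicts protocol 9.6.1. Under a constant burden and uniform last-dose times, 10% drop-out moves an arm mean by about 0.063 x baseline, -0.19 to -0.63 unit for baselines of 3 to 10 units/12 weeks. With equal drop-out the difference is unbiased under the null. With a true effect it loses precision, and it is also diluted where stoppers would have shared that effect. With unequal drop-out it is biased towards the arm that stops more. Burden, SD and stop times are assumptions.

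A reader might infer three stronger things that the documents do not support:
- **That the submitted result is inflated in favour of luspatercept.** The handling actually used and the drop-out by arm are not given, and the bias can run either way.
- **That every early stopper counts as a 100% reduction.** That needs a last dose by Day 65; the loss shrinks after that and is nil from Day 149.
- **That the primary endpoint or key secondaries 1 to 3 share the artefact.** The conflict over records reaches them, but the non-responder rule keeps uncounted time from passing as benefit.

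This should be corrected; it does not threaten the trial's main conclusion.

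**What to change.** 1. For endpoint 4 and the by-interval change summaries in SAP 10.3, count all collected transfusion records through the end of the window regardless of treatment status, as protocol 9.6.1 states.
2. For subjects whose window is still not fully observed, state one rule before the re-run, for example multiple imputation or baseline carried forward, with a sensitivity analysis. Baseline carried forward matches the spirit of the non-responder rule but is a single imputation and open to debate. Scaling by 84/observed days must not be used when no window day is observed, since it is then undefined.
3. Report how many windows were truncated in each arm and how the completed analysis handled them.
4. Present the re-run as a labelled supplementary analysis beside the submitted result, not as a replacement.

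The cost is SAP wording, one added ANCOVA with its sensitivity analysis, and the related tables. The downside is small: the re-run comes after unblinding and has to be labelled so. The planned collection to Week 48 extends beyond Day 169, so no new data collection is needed.

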5.2 Analysis Populations

5.2.1 Intent-to-Treat Population

The intent-to-treat (ITT) population consists of all randomized subjects regardless of whether or not the subject received IP. All efficacy analyses will be conducted for the ITT population and will be analyzed based on randomization group.

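### The 24- and 48-week total transfusion-burden summary keeps only an on-treatment subset, although later transfusions were recorded, so its by-arm means may be biased

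*SAP*

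**What the plan says.** After the four key secondary endpoints, SAP Section 10.3 describes a summary of the total reduction in transfusion burden. Baseline is the 24-week total (12 historical weeks plus 12 run-in weeks), doubled for the 48-week comparison. Descriptive statistics and change from baseline are given by arm at 24 and 48 weeks, with the restriction "Only subjects whose efficacy cutoff date was on or beyond end of the week 24/48 interval were included in the analysis".

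SAP Section 10 defines the cutoff for the primary report as the "minimum date among death date, study discontinuation date, last dose date + 20, and 11MAY2018". For subjects who stopped treatment early, the same section says that "the transfusion records were collected up to 48 weeks or 9 weeks post last dose, whichever was the later date". It then limits what is used: "All the transfusion records collected throughout the entire study period up to the efficacy cutoff date were used in the RBC related efficacy analyses".

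Three other statements bear on this:

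- Protocol Section 9.6.1, on early-discontinued subjects: "the transfusion records will still be collected up to 48 weeks. All the transfusion records will be used to evaluate primary and secondary endpoints". Protocol Section 6.6.1 and footnote 24 of Table 3 set out the matching collection rule.
- SAP Section 5.2.1: "All efficacy analyses will be conducted for the ITT population". The opening of Section 10 repeats this and names quality of life as the only exception.
- SAP Section 10, on the responder endpoints: a subject whose cutoff falls before the end of the 12-week interval stays in the analysis as a non-responder.

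**The concern.** Whether a subject enters this summary is decided after randomisation, by how long treatment lasted. The two arms shown are therefore not the randomised arms, and the mean reduction describes those who continued. The outcome for most excluded subjects is not missing: their transfusions were to be recorded to Week 48 and are set aside by the cutoff.

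The responder analyses count an early stop as failure, whereas this summary leaves the subject out, and Section 10.3 does not call the result on-treatment. It is the summary that speaks directly to total units saved over 24 and 48 weeks. SAP Section 2 says that completed analyses go into the final report without being updated, so an unlabelled figure would be carried forward. At stake is how that descriptive figure is read, not a test result.

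**Working it through.** **The plan's own figure.** The documents give no target or result for this summary. The nearest usable input is the 10% drop-out per arm in SAP Section 4.4. That sample size reproduces with a continuity-corrected two-proportion formula (40% against 20%, 2:1, two-sided 0.05, 90% power): 180 + 90 = 270, and 270/0.90 = 300. It does not otherwise bear on this point.

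**Step 1: who is excluded.** Inputs: doses every 21 days (Protocol Section 7.2), last dose + 20 days (SAP Section 10), interval ends at Day 169 and Day 337 (SAP Section 5.1). For on-schedule dose k, dosing day = 1 + 21(k − 1) and cutoff = dosing day + 20.

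| Last dose | Day given | Cutoff | Interval end | Included? |
|---|---|---|---|---|
| 8 | 148 | 168 | 169 | No, by 1 day |
| 9 | 169 | 189 | 169 | Yes |
| 16 | 316 | 336 | 337 | No, by 1 day |
| 17 | 337 | 357 | 337 | Yes |

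The last dose must fall on or after Day 149 (169 − 20) or Day 317 (337 − 20). Without delays, Dose 17 belongs to the Long-term Treatment Period (Protocol Table 3). An on-schedule subject who takes all 16 doses and does not continue is therefore left out of the 48-week summary. By the formula in SAP Section 9.1 that subject was treated for (336 − 1 + 1)/7 = 48.0 weeks. A sixteenth dose given one day late, within the ±3-day window of Protocol Section 6.2, would bring the subject in.

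**Step 2: possible size.** Let q be the share excluded, c the mean change in included subjects and d the mean change in excluded subjects, with subscripts L and P for the arms and negative values meaning fewer units.

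Restricted difference = cL − cP

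All-randomised difference = [(1 − qL)cL + qL·dL] − [(1 − qP)cP + qP·dP]

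All-randomised minus restricted = qL(dL − cL) − qP(dP − cP); a positive value means the restricted version overstates the benefit.

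The documents give none of these quantities. Assume for illustration cL = −3, cP = 0 and 10% excluded in each arm, which is 20 + 10 = 30 of 300 subjects at the planned numbers. The restricted difference is then −3.0 throughout.

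| dL | dP | All-randomised | Restricted relative to all-randomised |
|---|---|---|---|
| 0 (no benefit kept) | 0 | −2.70 | 3/2.70: +11.1% |
| −1.5 (half kept) | 0 | −2.85 | 3/2.85: +5.3% |
| −3 (all kept) | 0 | −3.00 | 0% |
| 0 | +3 | −3.00 | 0% |
| 0 | +6 | −3.30 | 3/3.30: −9.1% |

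When excluded placebo subjects behave like included ones, the ratio is 1/[(1 − q) + qk], where k is the fraction of benefit kept. The percentages in the first three rows then do not depend on the choice of −3.

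**The case against.** A reader might infer that the benefit is overstated. The documents do not support that as a fact. The filter applies to both arms, and there are no discontinuation rates or off-drug burdens to fix its direction. Protocol Section 1.3.2.1 itself anticipates that control subjects may leave for lack of response; losing placebo subjects who did badly pushes the other way, as the last two rows of the second table show.

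The larger figures also need extreme inputs. Because the quantity is a cumulative total, keeping none of the benefit means gaining nothing even while dosed; a subject who stops at Week 40 brings 40 treated weeks to the 48-week total. Subjects excluded by one day after 16 doses fit neither k = 0 nor k = 0.5. An overstatement of 25% needs 20% excluded with nothing kept, and 20% has no source in the documents. Even 10% is a sample-size allowance, not a forecast of exclusions.

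Other points carry weight. The totals are not listed among the visible endpoints in Protocol Table 2 or SAP Section 4.2, so the protocol's promise about primary and secondary endpoints reaches them only indirectly. Section 10.3 states the subset openly and reports n. The disposition table (SAP Section 6) gives completion and reasons for stopping by arm. Burden is also summarised for each 12-week interval to Week 48 without this stated restriction, although Section 10 still limits the records to the same cutoff. The analysis is written as completed, so any addition comes after unblinding.

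These points reduce the weight of the concern and remove any claim about direction. They do not remove the on-treatment selection or the departure from the general ITT statement, and n alone does not show why subjects are absent.

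**Conclusion.** The point stands in limited form. The 24- and 48-week totals describe an on-treatment subset chosen by a post-randomisation event. They omit early-discontinued subjects whose transfusions were to be collected, and they can omit subjects who received every scheduled dose. This departs from the SAP's own ITT statement.

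The by-arm mean reduction may be biased. Overstatement is plausible, because the amendment rationale for stopping routine collection 9 weeks after the last dose treats the drug as having no effect beyond then. At 10% excluded it would be about 5% to 11% if excluded luspatercept subjects keep half or none of the benefit and excluded placebo subjects resemble the rest. Under other assumptions it is nil or reversed.

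A reader might also infer that the trial's main results are affected. This sentence does not do that: the summary has no test or confidence interval and lies outside the gatekeeping sequence.

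**What to change.** Add the 24- and 48-week totals for all randomised subjects, using every recorded transfusion to Day 169 and Day 337 whether or not the subject was still on treatment. State a method for subjects without records to the interval end, for example a rate over observed days. Report the number excluded from the present summary by arm and reason, showing separately those who miss by one day after Dose 8 or Dose 16. Keep the present version as supportive and label it on-treatment.

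The cost is one supplementary table from data already collected. It must be identified as added after the primary analysis, and the figure may come out slightly less favourable.
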